1.4. Sample Size

The Population of the study consisted of patients with kidney stones who will undergo ESWL. The sample size was calculated based on the statistical diagnosis of the study which is, comparative analysis of independent two groups. A total of 70 subjects were planned to be included in the study, 35 of which were intervention while the rest were placebo. Patients were randomly assigned to both groups in this study.

1.5. Ethical Approval

Approval for the study was granted by the Research Ethics Committee Faculty of Medicine, Udayana University (Number: 1637/UN14.2.2.VII.14/LT/2020). Verbal and written informed consent was obtained from all subjects in the study.

Author Contributions

Conflict of Interests

The Authors have no conflict of interests to declare

Acknowledgements

The authors thank all those participated in this study.

Financial Disclosure

STATISTICAL ANALYSIS PLAN (SAP)

Data collected in this study were analysed statistically using SPSS for Windows software 25. Data were analysed by descriptive statistics to describe the characteristics of the subjects based on the treatment group and presented in the form of a distribution table. The compatibility of the variables on the numerical data scale uses the average comparison with the independent t-test. The categorical-scale variables used the proportion comparison with chi-square test. The limit value of significance was set at 0.05. The normality data assessment in this study is based on the central limit theorem, where the sample size in each group more than 30 makes the z distribution close to the t distribution and the data will be normally distributed. Bivariate and Multivariate analyses were performed using repeated measure ANOVA to control covariates. The value of the limit of significance is set to 0.05.

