1.1. Study Design and Patient Selection

This study was designed as a randomized, double-blind placebo-controlled trial to assess the effect of allopurinol administration in reducing tubular damage, vascular dysfunction and focal zone biophysical changes in the kidney due to ESWL.

Patients were randomly assigned to the intervention and placebo groups in this clinical study. The study group was formed of patients with kidney stone who undergo ESWL.

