1.2. Process and Intervention

Patients with kidney stones who will undergo ESWL were randomized into 2 groups. Group 1 was given allopurinol, and group 2 was given a placebo. Allopurinol 300 mg was administered orally for a total of 3 days, starting from the day before ESWL. Malondialdehyde (MDA), nitric oxide (NO), kidney injury molecule-1 (KIM-1) in urine were measured by technique quantitative double antibody sandwich direct ELISA before ESWL, continued two hours, and 24 hours after ESWL. Changes in the interlobar artery resistive index (RI) were assessed together with measurements of shear wave velocity (SWV) values in the renal focal zone before ESWL, followed by two weeks, and four weeks after ESWL.

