1.3. Safety Evaluation

If there was any drug side effects or serious adverse events(SAE), the subjects were reported to the ethics committee as soon as possible, less than 24 hours from the first time they were discovered, and actions were carried out as quickly as possible until the series of events ends. SAE was written in detail on the SAE form, including the following; when it was first discovered, the manifestation of the incident, the conditions before the incident, the handling of the event, and the outcome.

If the subject experiences side effects such as allergic reactions (redness of the skin, swelling of the eyes or mouth) and severe gastrointestinal disturbances (vomiting, diarrhea), the subject will be excluded from the analysis. The subject will also be excluded from the analysis if the subjects experience complications related to ESWL

procedure such as ureteral obstruction, pain (VAS > 5), or there were signs of infection. Subjects will be evaluated when visiting the hospital according to schedule, telephone contact, or by making a home visit.

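### The SAP's rule that more than 30 patients per group makes the data normal is false and takes the place of any check of scale or residuals; how much this costs depends on distributions the documents do not give

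*Combined protocol and SAP*

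**What the plan says.** The SAP section handles normality in one sentence. It begins "The normality data assessment in this study is based on the central limit theorem", sets the condition "where the sample size in each group more than 30", and concludes that this "makes the z distribution close to the t distribution and the data will be normally distributed". The next sentence names the main model: "Bivariate and Multivariate analyses were performed using repeated measure ANOVA to control covariates". An independent t-test is also named for numerical variables, with a significance limit of 0.05. No analysis scale, transformation, residual check, sphericity correction or non-parametric alternative appears anywhere.

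The numerical outcomes are in section 1.2. MDA, NO and KIM-1 "in urine were measured by technique quantitative double antibody sandwich direct ELISA before ESWL, continued two hours, and 24 hours after ESWL"; RI and SWV are measured before ESWL and at two and four weeks. Section 1.1 gives the premise, that allopurinol is tested for "reducing tubular damage, vascular dysfunction and focal zone biophysical changes in the kidney due to ESWL". Section 1.4 states "A total of 70 subjects were planned to be included in the study, 35 of which were intervention while the rest were placebo", without power, effect size or SD. Section 1.3 removes some patients from the analysis, for example: "The subject will also be excluded from the analysis if the subjects experience complications related to ESWL".

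**The concern.** The rule confuses the distribution of a mean with the distribution of the data. A sample of 35 from a skewed population is still skewed, and a larger sample only shows this more clearly. The rule is also the plan's whole assessment, so it removes the step at which someone would ask on which scale a urine concentration should be analysed. Such a concentration cannot be negative and may vary multiplicatively.

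Two things are at stake. One is power, if the chosen scale suits the data badly. The other is the false-positive rate of the group-by-time test, if the spread of the data differs between visits and no correction is applied. In addition, the rule's own condition is not secured: 35 − 5 = 30, so five exclusions in one arm (5/35 = 14%) leave it short of more than 30.

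**Working it through.** **1. The plan's figure.** 35 per arm cannot be reproduced, because its inputs are not stated. Solved backwards for a two-sided 0.05 t-test with 80% power: d = (1.960 + 0.842) × √(2/35) = 2.802 × 0.239 = 0.67. The simulations below use 0.68 log-SD, nearly the same effect.

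**2. Is the rule true?** For a lognormal variable with log-SD s, skewness = (e^(s²) + 2) × √(e^(s²) − 1). Sample size does not enter.
- s = 0.5: 3.284 × 0.533 = 1.75
- s = 1.0: 4.718 × 1.311 = 6.18

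Only the mean improves with n: its skewness is divided by √n, giving 1.75/5.92 = 0.30 and 6.18/5.92 = 1.04 at n = 35. In simulated lognormal samples of 35, Shapiro-Wilk rejects normality in 79% at s = 0.5 and 99.8% at s = 1.0. With n = 350 it rejects in 99.9% even at s = 0.25.

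**3. Test and assumptions.** From the documents: 35 per arm, three urine samples per patient, alpha 0.05. Assumed, because the documents are silent: two-sided test; within-patient log correlation 0.5; allopurinol effect of 0.68 log-SD at 2 h and 24 h only; no covariates. The group-by-time statistic is F = (SS_group×time / 2) / (SS_residual / 136), where 136 = (70 − 2) × 2. Greenhouse-Geisser multiplies both degrees of freedom by the estimated ε. Each lognormal setting had 10,000 trials or more.

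**4. Power, lognormal data, sphericity assumed.**

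| log-SD | Raw, equal 2- to 5-fold rise | Raw, no rise | Log |
|---|---|---|---|
| 0.5 | 85–87% | 68% | 83–84% |
| 0.8 | 73–75% | about 51% | 84% |
| 1.0 | 60–64% | 43% | 84% |

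At log-SD 0.3 with the rise, raw is slightly better (88–90% against 84%). At log-SD 0.5 with a 4- to 5-fold peak at 2 h, raw power under Greenhouse-Geisser is about 77% against 83% on the log scale. So mild skewness costs nothing under an equal rise, but can cost power under other time courses.

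**5. Power, gamma data, equal 2- to 5-fold rise** (same correlation through a Gaussian copula, log-shift 0.68 × CV). Raw against log:
- CV 0.5: 90–92% against 78–79%
- CV 0.8: 88–90% against 68–69%
- CV 1.0: 86–88% against 60–61%

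The ranking is reversed. With no rise the two scales lie within a few points of each other.

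**6. Type I error, lognormal data, raw scale.** With an equal rise it is about 4–5%: two equal arms with the same distribution give a symmetric difference, so the skewness cancels. With an early peak, raw SD grows in proportion to the median, so the visits have unequal spread and sphericity fails. Over patterns such as 3-fold then 1.5-fold, 5-fold then 2-fold, and 4-fold then back to baseline, the uncorrected test runs at about 5.4–7.8%. Greenhouse-Geisser brings it to 3.7–4.9%.

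**7. The threshold of 30.** Assume independent exclusions at one rate in both arms. P(5 or more of 35) is 0.029, 0.269 and 0.619 at exclusion rates of 5%, 10% and 15%. The chance that at least one arm falls to 30 or fewer is 1 − (1 − p)²: about 6%, 47% and 86%. The documents give no exclusion rate.

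**The case against.** The strongest reply is that the sentence is loose wording for something defensible: with 35 per arm, t and F tests on means are fairly robust. Much of this stands. With equal rises the tests hold their level, and the documents do not show that any marker is strongly skewed. Every input that produces a power loss is assumed, and on gamma data with a rise the log scale would lose about 26 points at CV 1.0. The sentence as written is still false, however, and robustness of the level does not choose a scale.

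Three further points stand in part.
- The SAP assigns no outcome to a model and says the ANOVA controls covariates, whereas the simulations have none. The power figures are therefore illustrations, not forecasts.
- The chance of an arm falling to 30 or fewer is secondary. The rule is wrong at any sample size, so missing its threshold changes little.
- Much of the text is in the past tense, so the treatment code may already be broken. That changes which fix applies, not whether the sentence is wrong.

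A reader might infer that a false normality rule makes the planned tests invalid. The working does not support this: non-normality alone did not inflate type I error. The excess appears only with unequal spread across visits and no correction.

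**Conclusion.** The point holds in a limited form. It is certain that the normality sentence is wrong and that the documents put nothing else in its place. The consequence is conditional: about 20 to 24 points of raw-scale power (84% against 60–64%) for lognormal markers at log-SD 1.0 with an equal rise, about 10 points at log-SD 0.8, and about 41 points at log-SD 1.0 with no rise (84% against 43%). These figures rest on the assumed distribution, correlation, effect and time course.

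Two further inferences go too far. One is that the log scale is right for these markers: the gamma results contradict it, and the documents give no distribution from which to decide. The other is the reassurance that type I error always holds, or that mild skewness never costs power. Both depend on the rise being equal at 2 h and 24 h, which the documents do not say.

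This is worth correcting because it is cheap and bears on the main model. It is not grounds for calling the trial's analysis invalid.

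**What to change.** Delete the statement that the data will be normally distributed. In its place:

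- State the analysis scale for each of MDA, NO, KIM-1, RI and SWV before the treatment code is broken, and say that model residuals will be examined for each on blinded pooled data.
- Report the group-by-time test with the Greenhouse-Geisser correction.
- For each urine marker, define one sensitivity set: the analysis on the other scale (log, as geometric mean ratio with 95% CI, if raw is primary; raw if log is primary), plus a rank-sum test of change from baseline at 2 h and at 24 h. With an equal 2- to 5-fold rise, the rank-sum test has 79–88% power for the lognormal settings and 77–86% for the gamma settings; with no rise it has less.

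Do not impose log as the default, and do not let a blinded skewness comparison choose the scale. In the gamma simulations such a rule still chose log in 92–98% of trials and recovered only about 1 point of power.

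If the code is already broken, keep the planned raw-scale result with the Greenhouse-Geisser p-value beside it, and label the log-scale and rank analyses post hoc.

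The cost is SAP wording or a labelled re-analysis of existing data. There is a little more to report, and values below the assay limit need a stated rule. Raw-scale power is slightly lower under the correction: with an equal rise on lognormal data, 57–59% at log-SD 1.0 and 70–73% at 0.8.

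### Five outcomes are each tested at 0.05 with no primary outcome, no multiplicity rule and no named ANOVA treatment effect, so 0.05 does not bound the error of the trial's conclusion

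*Combined protocol and SAP*

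**What the plan says.** Section 1.1 sets a three-part aim, the effect of allopurinol in "reducing tubular damage, vascular dysfunction and focal zone biophysical changes in the kidney due to ESWL", and ranks none of the parts.

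Section 1.2 lists the measurements. For urine: "Malondialdehyde (MDA), nitric oxide (NO), kidney injury molecule-1 (KIM-1) in urine were measured", at three times, "before ESWL, continued two hours, and 24 hours after ESWL". For imaging: "Changes in the interlobar artery resistive index (RI) were assessed together with measurements of shear wave velocity (SWV) values in the renal focal zone", again at three times: pre-ESWL, two weeks and four weeks. That makes five outcomes with three time points each, on two different schedules.

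Section 1.4 plans 70 subjects, 35 per arm, and explains: "The sample size was calculated based on the statistical diagnosis of the study which is, comparative analysis of independent two groups". It names no outcome, effect size, SD or power.

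The SAP is one paragraph. After the t-test and chi-square comparisons it states "The limit value of significance was set at 0.05", and for the repeated measurements "Bivariate and Multivariate analyses were performed using repeated measure ANOVA to control covariates. The value of the limit of significance is set to 0.05". It gives no testing order, adjustment or success rule.

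**The concern.** The allopurinol-placebo comparison itself is clear. Three things are not: which outcome carries the conclusion, how significance is controlled across the five, and which ANOVA effect tests treatment. The sample-size section cannot fill the first gap, because it is tied to no outcome.

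Two consequences follow. With five chances at 0.05, one significant marker is weaker evidence than its p-value suggests, and a reader cannot tell how much weaker. Separately, the group and group-by-time effects can differ widely in power on the same data. Leaving the choice open allows it to be made after the results are known, and a multiplicity rule across outcomes would not by itself prevent that.

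**Working it through.** **Plan's own figure.** The 35 per arm cannot be reproduced, because no effect size, SD or power is given. Working backwards at two-sided 0.05 and 80% power, d = (1.960 + 0.842) × √(2/35) = 0.67, or 0.68 with the t distribution. It is used below only as an assumed effect.

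**Error across outcomes.** From the documents: k = 5 outcomes and a 0.05 limit. Assumed: two-sided testing, one 1-df test per outcome, a favourable direction defined for each, no true effect, and a common correlation r between test statistics.

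- Independent, favourable direction: 1 − 0.975^5 = 0.119. Either direction: 1 − 0.95^5 = 0.226.
- Correlated, favourable direction: 1 − E[Φ((1.96 − √r·U)/√(1 − r))^5], with U standard normal. The either-direction version uses both tails.

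| Reading | r = 0 | r = 0.7 | r = 0.9 | One test |
|---|---|---|---|---|
| Any of five, favourable | 11.9% | 7.4% | 5.1% | 2.5% |
| Any of five, either direction | 22.6% | 14.8% | 10.2% | 5% |
| Any of three (one per domain), favourable | 7.3% | 5.5% | 4.2% | 2.5% |
| All five favourable | under 0.1% | 0.2% | 0.8% | 2.5% |

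A simulation of five two-sample t-tests with 35 per arm agrees with the first row: 12.2% at r = 0 and 5.2% at r = 0.9.

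The first row is not a ceiling. If two visits per outcome could each count, there would be ten tests, and with independence 1 − 0.975^10 = 22.4%.

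**Choice of effect.** Assumed: a difference of 0.68 SD at both post-ESWL times and none before, unit SD at each visit, equal within-person correlation ρ, all 35 per arm analysed, √(35/2) = 4.18.

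- Group effect (mean of three visits): difference 0.68 × 2/3 = 0.453, variance (1 + 2ρ)/3. Noncentrality 0.453 × 4.18/√variance = 2.60, 2.32 and 2.12 at ρ = 0.3, 0.5 and 0.7 (t, 68 df).
- Group-by-time: sum of squared deviations 0.453² + 2 × 0.227² = 0.308. Noncentrality 17.5 × 0.308/(1 − ρ) = 7.7, 10.8 and 18.0 (F, 2 and 136 df).
- Mean of the two post-ESWL values adjusted for the pre-ESWL value: residual variance (1 + ρ)/2 − ρ² = 0.56, 0.50 and 0.36. Noncentrality 0.68 × 4.18/√variance = 3.80, 4.02 and 4.74 (t, 67 df).

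| Power at ρ = 0.3 / 0.5 / 0.7 | at 0.05 | at 0.01 |
|---|---|---|
| Group | 73 / 63 / 55% | 48 / 38 / 31% |
| Group-by-time | 69 / 84 / 97% | 45 / 64 / 90% |
| Baseline-adjusted contrast | 96 / 98 / over 99% | 87 / 91 / 98% |

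Allowing for chance baseline imbalance, the 87% becomes about 86%.

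**Remedy check.** Holm's first step with five outcomes is 0.05/5 = 0.01. The chance of any false favourable result is then 1 − (1 − 0.005)^5 = 2.5% at r = 0, and by simulation 1.7% at 0.7 and 1.2% at 0.9. A named primary gating the other four, opened only by a favourable primary result, gives 2.5%.

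**The case against.** The strongest reply is that the documents never say one positive marker would count as success. Section 1.1 only sets out to assess the effect. A reader might infer from the table that this trial has a 12%, or even 23%, false-positive rate. The documents do not support that: success rule, sidedness and correlation are all unstated, and requiring all five would mean no inflation. This stands, and the percentages are illustrations.

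A reader might equally take 5% to 12% as the full range. That fails too, because it assumes one test per outcome while the plan leaves the effect open. Moreover, with three time points the group-by-time test has 2 df and no direction, so a favourable result at 0.025 is undefined for it without a further rule. The documents also state no favourable direction for any marker, NO included. This objection stands and shapes the fix.

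It could be said that the word *multivariate* means a joint test of all five outcomes. The SAP attaches it to the control of covariates, the two sets of outcomes follow different schedules, and no joint test is described as a gate. That reading does not hold.

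Finally, nothing labels the trial confirmatory, and reporting five biomarker and imaging measures as exploratory is legitimate. But the SAP does not say that either.

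**Conclusion.** The omission is certain on the text of sections 1.1 to 1.5 and the SAP; the opening front matter was not available. As written, 0.05 is a per-test limit and the error of the overall conclusion is undefined.

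Under the any-one-of-five reading, a false favourable result is about two to five times as likely as with a single test (5.1/2.5 to 11.9/2.5). That rests on the assumptions listed in the working, none of which the documents supply. The choice of ANOVA effect matters in its own right: under the assumed effect, power for group against group-by-time is similar at within-person correlation 0.3 and far apart at 0.7 (55% against 97%).

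This should be corrected, but it does not show that the trial's conclusion would be wrong. Nor do the documents show that the investigators intend to select a favourable result.

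**What to change.** In the SAP:

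1. **One treatment test for every outcome.** Use the allopurinol-placebo difference in the mean of the two post-ESWL values, adjusted for the pre-ESWL value. It has 1 df and a direction. State the favourable direction for each marker. First confirm that the pre-ESWL value precedes the first dose: section 1.2 has the drug "administered orally for a total of 3 days, starting from the day before ESWL" and does not say when the sample or scan is taken. A value taken after dosing is not a baseline, and adjusting for it could remove part of the effect.
2. **One multiplicity rule.** Either name one primary outcome at two-sided 0.05 before data are seen by group, and test the other four by Holm at 0.05 only if the primary significantly favours allopurinol; or apply Holm at 0.05 across all five.
3. **If data have already been seen by group**, which the SAP's past tense leaves open, apply Holm across all five, report all five and label them exploratory.

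**Cost.** Wording only, if data have not been seen by group; otherwise, confirmatory status. Holm costs power at its strictest step (0.01): under the assumed effect the recommended contrast drops from 96%, 98% and over 99% to about 86%, 91% and 98%. Keeping either planned ANOVA effect would cost more, as the power table shows. The exclusions from analysis in section 1.3 would lower all these figures. A named primary keeps the full 0.05, but the other four outcomes cannot be claimed if it fails.

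### The SAP does not say which repeated-measures ANOVA term tests treatment or how the pre-ESWL value enters; one treatment test should be named in advance, with a pre-dose baseline used as a covariate

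*Combined protocol and SAP*

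**What the plan says.** Section 1.2 sets the measurement schedule. Urinary MDA, NO and KIM-1 are measured by "ELISA before ESWL, continued two hours, and 24 hours after ESWL". RI and SWV are assessed together, the latter "in the renal focal zone before ESWL, followed by two weeks, and four weeks after ESWL". So there are five outcomes, each with one pre-ESWL and two post-ESWL values, and none is called primary.

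The SAP then says: "Bivariate and Multivariate analyses were performed using repeated measure ANOVA to control covariates". The covariates are not listed. The SAP also mentions an independent t-test for numerical variables, but gives no time point for it, and the wording may refer only to comparability of the groups. On the threshold it says "The value of the limit of significance is set to 0.05", without stating whether tests are one- or two-sided.

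On dosing, section 1.2 says the drug is "administered orally for a total of 3 days, starting from the day before ESWL". It does not say whether the pre-ESWL measurements come before or after the first dose.

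**The concern.** A two-group, three-time repeated-measures ANOVA gives two terms that could be read as the treatment test: the group main effect and the group-by-time interaction. They answer different questions and can have very different power on the same data. With neither named, the choice can be made after the data are seen.

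The role of the pre-ESWL value matters as well. As a third time level, it enters the group mean at a time when treatment should have had no effect, so the main effect is diluted. In the interaction it is used by subtraction, which is less efficient than adjusting for it as a covariate. The value is already collected, so better use of it costs almost nothing.

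A baseline covariate is sound only if treatment has not yet affected it. Dosing begins before ESWL, so a sample described only as pre-ESWL could be pre-dose or post-dose.

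**Working it through.** **No plan figure to reproduce.** Section 1.4 gives 70 subjects, "35 of which were intervention while the rest were placebo", and bases this on a "comparative analysis of independent two groups". It states no effect size, SD or power, so 35 per arm cannot be re-derived. The figures below are illustrations.

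**Inputs.** From the documents: n = 35 per arm, significance level 0.05, one pre-ESWL and two post-ESWL values. Assumed: two-sided tests, all 35 per arm analysed, SD 1 at each time, compound symmetry with correlation ρ = 0.3, 0.5 or 0.7, and no group difference before ESWL. The reference effect of 0.68 SD is the one at which a plain t-test with 35 per arm has 80% power.

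**Formulas.** Effects over the three times are e = (0, d1, d2), and d = (d1, d2).

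- Main effect (three levels): noncentrality (n/2)·mean(e)² / [(1+2ρ)/3]; F on 1 and 68 df.
- Group-by-time: (n/2)·Σ(e − mean e)² / (1−ρ); F on 2 and 136 df.
- Baseline-adjusted joint test: (n/2)·d′S⁻¹d, where S has diagonal 1−ρ² and off-diagonal ρ−ρ²; F on 2 and 66 df.
- Baseline-adjusted mean of the two post values: (n/2)·mean(d)² / [half the sum of the diagonal and off-diagonal of S]; F on 1 and 67 df.

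**Worked case: sustained 0.68 SD, ρ = 0.5.**

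- Main effect: mean(e) = (0 + 0.68 + 0.68)/3 = 0.453, two thirds of 0.68. Noncentrality 17.5 × 0.2055 / 0.6667 = 5.39; power 63%.
- Group-by-time: Σ = 0.2055 + 2 × 0.0514 = 0.3083. Noncentrality 17.5 × 0.3083 / 0.5 = 10.79; power 84%.
- Adjusted joint: d′S⁻¹d = 2 × 0.4624 / (0.75 + 0.25) = 0.9248. Noncentrality 17.5 × 0.9248 = 16.18; power 95%.
- Adjusted mean: 17.5 × 0.4624 / 0.5 = 16.18 on 1 df; power 98%.

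Here 5.39 + 10.79 = 16.18: the adjusted joint test brings together information that the three-level ANOVA splits between two terms.

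**Power (%) at ρ = 0.3 / 0.5 / 0.7.**

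| Effect at the two post times (SD) | Main effect | Group-by-time | Adjusted joint | Adjusted mean |
|---|---|---|---|---|
| 0.68, 0.68 | 72.6 / 62.9 / 55.2 | 69.0 / 83.7 / 97.1 | 92.4 / 95.0 / 99.0 | 96.3 / 97.8 / 99.7 |
| 0.68, 0.23 | 40.3 / 33.5 / 28.8 | 57.3 / 72.8 / 92.2 | 75.0 / 82.8 / 94.7 | 70.8 / 75.6 / 87.8 |
| 0.68, 0 | 24.9 / 20.8 / 18.1 | 69.0 / 83.7 / 97.1 | 76.9 / 87.2 / 97.6 | 46.6 / 50.9 / 64.7 |
| 0.5, 0.5 | 46.9 / 39.1 / 33.6 | 42.2 / 56.1 / 79.4 | 68.5 / 73.8 / 87.2 | 78.7 / 83.0 / 93.0 |
| 0.4, 0.4 | 32.5 / 27.0 / 23.3 | 28.4 / 38.3 / 59.1 | 48.5 / 53.3 / 68.3 | 59.6 / 64.5 / 78.5 |

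For a sustained 0.68 SD effect, 80% power needs 25/23/17 patients per arm with the joint test and 45/33/20 with group-by-time. Simulation put the joint test's type I error at 5.0–5.2%. With AR(1) correlation in place of compound symmetry, the joint test gains 0 to 29 points over group-by-time in the three 0.68 SD patterns.

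**Claiming on either term.** Under compound symmetry the two ANOVA terms are independent, so the false-positive rate per outcome would be 1 − 0.95² = 9.75%. Simulation gave 9.7–10.0%.

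**If the pre-ESWL value is post-dose.** Suppose treatment has already shifted it by 0.2 SD. The adjusted effect becomes d − ρ × 0.2, which is too small by 0.06/0.10/0.14 SD. For a sustained 0.68 SD effect, joint-test power is 87/86/92% adjusted and 88/83/78% unadjusted. Leaving the value out therefore removes bias; it does not reliably add power.

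**The case against.** The omission itself is hard to dispute: no section supplies the deciding term or the role of the pre-ESWL value. The objections concern how much follows from it.

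- **The layout is assumed.** The SAP uses the ANOVA to control unnamed covariates. If the pre-ESWL value is among them and only the post values are repeated, the plan is already close to the fix and the gain is about zero. This stands.
- **The joint test is not the only answer.** A reader might infer that it must be the deciding test. The documents do not support that. They state no time course, and the aim in section 1.1 is directional (a reduction in damage), whereas a 2-df test has no direction and no single estimate. The adjusted mean or one named time point would also close the gap. This stands.
- **The joint test has a price.** It would be wrong to read the small loss at 0.68 SD as a general ceiling, because power there is near 100%. Under a sustained effect the joint test loses up to about 4 points to the adjusted mean at 0.68 SD, but 6–10 points at 0.5 SD and 10–11 at 0.4 SD. Against that, if a 0.68 SD effect fully fades, it gains 30 to 36 points.
- **The error rate is not shown to be inflated.** A reader might infer a 9.75% false-positive rate. That holds only if success may be claimed on either term, which the SAP does not say.
- **Disagreement is not contradiction.** The two ANOVA terms often differ in significance in these scenarios, but much of that reflects the lower power of a diluted main effect, not conflicting evidence.

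**Conclusion.** The concern holds in a limited form. The SAP leaves open the treatment term and the role of the pre-ESWL value. An unnamed term alone would be missing detail. What makes this a substantive point is that using an already collected baseline as a covariate is a better method than using it as a third time level.

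If the three-level layout was intended, the adjusted joint test has higher power than both ANOVA terms in every compound-symmetry case in the table. At 0.68 SD its gain over group-by-time runs from 23 points (sustained, ρ = 0.3) to 0.5 points (fully faded, ρ = 0.7). If the baseline is already a covariate, nothing is gained beyond clarity.

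The effect sizes, correlations and time patterns are all assumptions. The powers also assume 35 analysed per arm, while section 1.3 removes subjects with certain side effects or ESWL complications from the analysis. The documents do not show that the pre-ESWL sample is post-dose; they only fail to show that it is pre-dose.

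**What to change.** 1. State whether each pre-ESWL measurement was taken before the first dose.
2. For each outcome, model the two post-ESWL values with treatment, time and treatment-by-time. If its pre-ESWL value is pre-dose, add it as a covariate with a slope that may differ by time. SPSS MIXED with unstructured covariance will fit this. If the value is not pre-dose, leave it out.
3. Name one treatment test in advance. The joint 2-df test of treatment at the two post-ESWL times, baseline-adjusted where step 2 allows, is a reasonable default because no time course is stated. The adjusted mean of the two times is the alternative if a sustained effect is expected.
4. Report the adjusted difference with its 95% CI at each post-ESWL time. This supplies the direction that the joint test lacks.
5. List any other covariates.

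The cost is SAP wording and one statement of sample timing; software, visits and assays stay the same. Patients without a pre-ESWL value drop out of the adjusted model. The SAP is written in the past tense, so if results have been seen the change must be labelled post hoc. This does not deal with multiplicity: five outcomes each tested at 0.05 give up to 1 − 0.95⁵ = 22.6% familywise error if independent, and that needs its own solution.
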